1.3 Number of participants

A sample size of 216 participants (72 participants per treatment group), randomised 1:1:1 to MEDI3506 **CC1** mg: MEDI3506 **CC1** mg: placebo, will provide at least 80% power to detect a statistically significant difference in change from baseline to Week 16 in pre-BD FEV₁, assuming a difference of 150 mL between placebo and MEDI3506, a between-participant SD of 420 mL and a one-sided- 10% alpha level. To allow for 5% participants being ineligible for the primary analysis, a total of approximately 228 participants will be randomised in the study (approximately 76/arm).

Up to 60 participants are intended to be included in the cough sub-study (approximately 20 participants per treatment group). However, given the exploratory nature of the sub-study and that it may not be activated in all countries, randomisation of participants not included in the sub-study will not be restricted, therefore, sub-study recruitment may not be achieved. Since limited data are available on cough monitoring in this population, the sub-study is considered exploratory and no formal power calculations have been performed.

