4.1.1 Statistical Hypotheses

The primary efficacy endpoint is the change from baseline in pre-BD FEV₁ at Week 16. A treatment policy estimand will be applied whereby all available data are included in the analysis, irrespective of whether a participant discontinued study intervention or received rescue therapy.

The null hypothesis is that the change from baseline in FEV₁ at Week 16 for participants dosed with MEDI3506 is equal to the change from baseline in FEV₁ at Week 16 for participants dosed with placebo. The alternative hypothesis is that the change from baseline in FEV₁ at Week 16 for participants dosed with MEDI3506 is greater than the change from baseline in FEV₁ at Week 16 for participants dosed with placebo, i.e.:

- H₀: Change from Baseline in FEV₁ at Week 16 (MEDI3506-placebo) = 0.
- H₁: Change from Baseline in FEV₁ at Week 16 (MEDI3506-placebo) > 0.

Hypothesis testing will be performed at the one-sided 10% level. If the p-value is < 0.1, reject H₀ and accept H₁. A hierarchical testing strategy will be used to preserve the type I error for the comparisons of each of the 2 dose levels of MEDI3506 versus placebo, as follows:

- Step 1: Test MEDI3506 **CC1** mg versus placebo in regard to H₀
- Step 2: If previous step rejects: test MEDI3506 **CC1** mg versus placebo in regard to H₀

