4.1.2 Repeated measures mixed effects analysis of covariance model (MMRM)

The repeated measures mixed effects analysis of covariance model (MMRM) will be used to fit change from baseline for continuous endpoints at each visit, for the ITT population. The model will include all available data from all visits up to and including the target visit, irrespective of whether the participant discontinued study intervention or received rescue therapy. No imputation will be made for missing data, as a repeated measures model is being applied. The model will include fixed effects for baseline, background medication use, geographic region, baseline ICS total daily dose, visit, treatment and the baseline by visit and treatment by visit interactions. Visits within subject are considered as repeated measurements. An unstructured covariance matrix will be used to describe the correlations between observations on a participant between visits. The denominator degrees of freedom will be calculated using the Kenward-Rogers method. In the event that the model with unstructured covariance matrix fails to converge, an autoregressive (1) covariance matrix will be used instead. If also the autoregressive (1) does not converge, a compound symmetry covariance matrix will be used. If the model still does not converge, the baseline by visit effect will be deleted from the model. Estimates of the least square mean change from baseline in endpoint variable for each treatment, and the difference between them, together with two-sided 80% confidence interval, will be obtained from the model for each visit. The significance of the treatment effect will be tested at a 10% one-sided level of significance as described in Section 4.1.1.

The reportable results from the model will be:

- The least-square means (LSMeans) change from baseline at certain visit and their standard errors for each group
- The difference in change from baseline at certain visit between active treatments groups and placebo (LSMeans difference) together with its two-sided 80% confidence interval (CI)
- The one-sided p-value for the difference in change from baseline at certain visit between active treatment groups and placebo

If the dependent variable is considered to be normally distributed, the variable fitted in the model will be the change from baseline; the MMRM and the reportable results will be those described above.

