4.2.6.6 Analysis of diary data and home spirometry

2-weekly mean asthma symptom score, 2-weekly mean rescue medication usage, 2-weekly mean night time awakening due to asthma, 2-weekly mean home FEV₁ and 2-weekly mean

home PEF as derived in Section 3.6.2 through Week 24 and the changes from baseline through Week 24 will be descriptively summarised using the ITT population.

Additionally, change from baseline will be analysed using MMRM (see Section 4.1.2). The LSmean changes from baseline and two-sided 80% CI through Week 24 will be presented in figures.

2-weekly means will be also reported in listing for the ITT population.

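### If the unstructured MMRM does not converge, the SAP falls back to covariance structures with one common variance and no robust standard error, so last-visit inference can be wrong in either direction

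*SAP*

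**What the plan says.** SAP 4.1.2 defines one MMRM for continuous endpoints measured at several visits. It uses an unstructured covariance, Kenward-Roger degrees of freedom and PROC MIXED. For non-convergence the rule is: "In the event that the model with unstructured covariance matrix fails to converge, an autoregressive (1) covariance matrix will be used instead". It continues: "If also the autoregressive (1) does not converge, a compound symmetry covariance matrix will be used". If that also fails, the baseline-by-visit term is dropped.

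The sequence contains no structure with visit-specific variances, and no empirical standard error is named anywhere in the section. Protocol 9.4.2.1 gives the fixed effects but no covariance structure.

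Several analyses cite this section: the primary analysis (SAP 4.2.4.1), the subgroup analyses of the primary endpoint (4.2.4.3), SNOT-22 (4.2.6.5), and the diary and home-spirometry endpoints through Week 24 (4.2.6.6). The model's outputs include two-sided 80% intervals and one-sided p-values. For the primary test, SAP 4.1.1 states: "Hypothesis testing will be performed at the one-sided 10% level".

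**The concern.** AR(1) and compound symmetry, as named, each have a single variance parameter. Under either one, the standard error of the Week 16 treatment difference is built from a variance pooled over all visits in the model. Kenward-Roger adjusts for estimating the covariance parameters within the chosen structure; it does not repair a structure that is wrong.

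If Week 16 is more variable than the average visit, the Week 16 interval is too narrow and the test rejects too often. If it is less variable, the reverse holds. The fallback goes straight from 15 covariance parameters to 2 in a five-visit model, or from 78 to 2 in a 12-period model, and skips the intermediate structures that would keep the variance free at each visit.

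For the primary endpoint, the nominal 10% level is at stake. For the other models, it is the accuracy of the reported intervals and p-values.

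**Working it through.** **Inputs from the documents.** SAP 1.3: "A sample size of 216 participants (72 participants per treatment group), randomised 1:1:1", "assuming a difference of 150 mL between placebo and MEDI3506" and "a between-participant SD of 420 mL and a one-sided- 10% alpha level". Post-baseline visits up to Week 16 are at Weeks 1, 4, 8, 12 and 16 (SAP 3.1.4). Diary data form 12 two-week periods (same section).

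**The plan's own figure.** SE = 420 × √(2/72) = 70 mL. Power = Φ(150/70 − 1.2816) = Φ(0.861) = 80.5%, which agrees with "will provide at least 80% power to detect a statistically significant difference". Randomised total: 216/0.95 = 227.4, so 228. The sample size is not affected by this point.

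**Size of the covariance matrices.** Five visits: 5 × 6/2 = 15 parameters. Twelve periods: 12 × 13/2 = 78.

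**Assumption.** Neither document gives an SD or correlation by visit. I hold Week 16 at 420 mL and let the earlier SDs rise, stay flat or fall.

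**Formula.** With complete data, the compound-symmetry variance tends to the mean of the visit variances. Let r = pooled SD / 420. Then:
- actual one-sided level = 1 − Φ(1.2816 r);
- coverage of the 80% interval = 2Φ(1.2816 r) − 1.

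Example, SD 300, 340, 375, 400, 420 mL: mean variance = (90,000 + 115,600 + 140,625 + 160,000 + 176,400)/5 = 136,525. Pooled SD = 369.5 and r = 0.880. The level is 1 − Φ(1.127) = 13.0%.

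| SD (mL) at Weeks 1, 4, 8, 12, 16 | Pooled SD | r | One-sided level | 80% CI coverage |
|---|---|---|---|---|
| 420 throughout | 420.0 | 1.000 | 10.0% | 80.0% |
| 380, 390, 400, 410, 420 | 400.2 | 0.953 | 11.1% | 77.8% |
| 300, 340, 375, 400, 420 | 369.5 | 0.880 | 13.0% | 74.0% |
| 460, 450, 440, 430, 420 | 440.2 | 1.048 | 9.0% | 82.1% |
| 500, 480, 460, 440, 420 | 460.9 | 1.097 | 8.0% | 84.0% |

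**AR(1).** The large-sample REML limit was computed under three assumed correlation patterns (exchangeable 0.6, autoregressive 0.8, and a mixed pattern). With complete data the results are almost the same; the steepest rise gives 13.0% to 13.1%.

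**Dropout.** With 0% to 15% monotone dropout, completely at random, across both fallbacks:
- steepest rise: 13.0% to 13.6%;
- equal SDs: 9.8% to 10.5%;
- steepest fall: 7.7% to 8.4%.

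**Finite-sample check.** There were 20,000 simulated three-arm trials per pattern, with 72 per arm, complete data and no covariates. The Monte Carlo error is about √(0.2 × 0.8/20,000)/2 = 0.14 percentage points.

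| Pattern | Pooled variance (compound symmetry) | Week 16 variance |
|---|---|---|
| Equal | 9.8% | 9.9% |
| Rise from 380 mL | 11.3% | 10.2% |
| Rise from 300 mL | 13.1% | 10.0% |
| Fall from 500 mL | 8.1% | 10.1% |

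**After the change.** With 5% dropout, heterogeneous AR(1) or heterogeneous compound symmetry gave 9.3% to 10.0% in every SD pattern.

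**The case against.** **The fallback may never be needed for the primary test.** That model has 15 covariance parameters for about 216 participants, and early-discontinuation and unscheduled visits are mapped into the windows (SAP 3.1.4). Suppose, purely for illustration, that it fails 1% to 10% of the time. Even the 13.1% case then adds only 3.1 × 0.01 = 0.03 to 3.1 × 0.10 = 0.31 percentage points to the overall level. This stands: a material effect on the primary decision is not shown.

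**Where failure is realistic, no error rate is controlled.** The hierarchical procedure in SAP 4.1.1 covers only the two dose comparisons on the primary endpoint. Diary, home-spirometry and SNOT-22 analyses are exploratory. This also stands, but the intervals are still reported, and the subgroup estimates go into a forest plot of the primary endpoint.

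**The visit SDs will be visible.** Changes from baseline are summarised by visit (SAP 4.2.4.1), so marked differences in spread would be seen. However, the SAP attaches no action to seeing them.

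**Unequal spacing.** AR(1) treats the clinic visits as equally spaced, although the first gap is 21 days (Day 8 to Day 29) and the later ones 28. The diary periods are all 14 days, so this does not apply to the largest models. The point does not rest on it.

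**A stronger reading.** A reader might infer that the fallback always makes Week 16 intervals too narrow and pushes the level above 10%. The best argument is that the model adjusts for baseline: if the FEV₁ SD is constant, residual variance is proportional to 1 − ρ², where ρ is the correlation with baseline, and ρ may weaken over time. That is plausible, but neither document gives ρ or any SD by visit. With equal or falling SDs the same rule is nominal or conservative.

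**Conclusion.** The point holds in conditional form. If the unstructured model fails and the variance differs between visits, the planned fallback misstates last-visit standard errors, p-values and 80% intervals, and nothing in SAP 4.1.2 corrects this. Over the SD patterns tried, the one-sided level ranges from about 8% to about 13% with complete data. The direction cannot be settled from the documents.

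These sizes rest on assumed SDs, with Week 16 at 420 mL, and were worked out only for a five-visit model of the primary type. No size was computed for the diary, SNOT-22 or subgroup models.

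Non-convergence of the primary model is unlikely, which is a judgement and not a figure from the documents. It is more realistic for:
- the 12-period models, with 78 parameters;
- SNOT-22, whose subset size is not stated;
- subgroups admitted at 20% of participants (SAP 3.1.7), about 0.20 × 216 = 43 people or 14 per arm.

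A modest correction is worth making; the primary analysis as planned is not undermined.

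**What to change.** In SAP 4.1.2, replace the fallback order for all MMRMs with: heterogeneous Toeplitz; then heterogeneous AR(1); then heterogeneous compound symmetry; and, only if all three fail, homogeneous compound symmetry with the empirical (sandwich) standard error. Name the degrees-of-freedom method for that last step, for example between-within. Removing the baseline-by-visit term can stay as the final resort. Report which structure was used for each model.

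Heterogeneous structures should come before the sandwich estimator for a second reason. The SAP relies on the MMRM in place of imputation, so with missing data a wrong covariance can also shift the point estimate. A sandwich standard error does not repair that. This effect was not sized here.

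The cost is one SAP sentence and a few SAS options. Sandwich standard errors can be somewhat small in small subsets, which is why they come last. Nothing changes where the unstructured model converges.

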4.1.3 Analysis of covariance (ANCOVA)

An ANCOVA model will be used to analyse change from baseline for continuous endpoints collected at only one post-baseline visit. The treatment group will be considered as a fixed effect of the model, with the baseline value, background medication use, geographic region and baseline ICS total daily dose as covariates. Comparisons of MEDI3506 **CC1** mg versus placebo and MEDI3506 **CC1** mg versus placebo will be assessed within the same model. The restricted maximum likelihood (REML) approach will be used for the estimation of the variance and covariance parameters of the linear model; one-sided difference test, with alpha level at 10% will be used for the treatment comparisons. No imputation will be made for missing data.

The reportable results from the model will be:

- The LSmeans and their standard errors for each treatment group;
- The difference between active treatment groups and placebo (LSmean difference) together with its two-sided 80% CI;
- The one-sided p-value for the difference between active treatment groups and placebo.

If the parameter results to be normally distributed, the variable fitted in the model will be the change from baseline; the ANCOVA model and the reportable results will be those described above.

On the other hand, if the parameter results to be log-normally distributed, the variable fitted in the model will be the change from baseline in logarithmical scale. Change from baseline in logarithmical scale is defined as the log-transformation of the post-baseline visit value minus the log-transformation of the baseline value.

The ANCOVA model will be as described above but the reportable results from the model will be:

- For the percent change:
 - Back transformed LSmeans for each group, which correspond to the estimated percent change from baseline; back transformed LSmeans is derived as $[\text{EXP}(\text{LSMean})-1]*100$;
 - Two-sided 80% CI of the back transformed LSmeans for each group; 80% CI of the back transformed LSmeans is derived as $[\text{EXP}(\text{Lower limit of the 80\% CI of the LSmean})-1]*100$; $[\text{EXP}(\text{Upper limit of the 80\% CI of the LSmean})-1]*100$;
- For the relative change:
 - Back transformed LSmeans for each group, which correspond to the estimated relative change from baseline; back transformed LSmeans is derived as $\text{EXP}(\text{LSMean})$;
 - Two-sided 80% CI of the back transformed LSmeans for each group; 80% CI of the back transformed LSmeans is derived as $\text{EXP}(\text{Lower limit of the 80\% CI of the LSmean})$; $\text{EXP}(\text{Upper limit of the 80\% CI of the LSmean})$;
- For the comparison:
 - The estimated geometric LSMean ratio between active groups and placebo; the ratio is calculated as $\text{EXP}(\text{LSMean difference})$;
 - The Two-sided 80% CI of the ratio; the 80% CI of the ratio is calculated as $\text{EXP}(\text{Lower limit of the 80\% CI of the LSmean difference})$; $\text{EXP}(\text{Upper limit of the 80\% CI of the LSmean difference})$;
 - One-sided p-value.

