On the other hand, if the dependent variable is considered to be log-normally distributed, the variable fitted in the model will be the change from baseline in logarithmical scale, with the logarithm of the baseline value as a covariate. Change from baseline in logarithmic scale is defined as the log-transformation of the post-baseline visit value minus the log-transformation of the baseline value.

The MMRM will be as described above but the reportable results from the model will be:

- For the percent change:
 - Back transformed LSmeans for each group, which correspond to the estimated percent change from baseline; back transformed LSmeans is derived as $[\text{EXP}(\text{LSMean})-1]*100$;
 - Two-sided 80% CI of the back transformed LSmeans for each group; 80% CI of the back transformed LSmeans is derived as $[\text{EXP}(\text{Lower limit of the 80\% CI of the LSmean})-1]*100$; $[\text{EXP}(\text{Upper limit of the 80\% CI of the LSmean})-1]*100$;
- For the relative change:
 - Back transformed LSmeans for each group, which correspond to the estimated relative change from baseline; back transformed LSmeans is derived as $\text{EXP}(\text{LSMean})$;
 - Two-sided 80% CI of the back transformed LSmeans for each group; 80% CI of the back transformed LSmeans is derived as $\text{EXP}(\text{Lower limit of the 80\% CI of the LSmean})$; $\text{EXP}(\text{Upper limit of the 80\% CI of the LSmean})$;
- For the comparison:
 - The estimated geometric LSMean ratio between active groups and placebo; the ratio is calculated as $\text{EXP}(\text{LSMean difference})$;
 - The Two-sided 80% CI of the ratio; the 80% CI of the ratio is calculated as $\text{EXP}(\text{Lower limit of the 80\% CI of the LSmean difference})$; $\text{EXP}(\text{Upper limit of the 80\% CI of the LSmean difference})$;
 - One-sided p-value.

Note that a ratio lower than 1 means that the active treatment group shows a higher decrease (or a lower increase) compared to the placebo group. On the other hand, a ratio greater than 1 means that the active treatment group shows a lower decrease (or a higher increase) compared to the placebo group.

The MMRM will be applied using PROC MIXED (SAS procedure).

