4.2.8.2 Analysis of blood biomarkers

Analysis of blood eosinophils

Blood eosinophils count will be summarised with descriptive statistics at each visit and change from baseline summarised for each post-baseline visit for the ITT population. Change from baseline in blood eosinophils will be analysed using MMRM as described in Section 4.1.2 for the ITT population. Endpoints will be log transformed prior to analysis. Estimates of the least square mean change from baseline for each treatment, and the difference between them, together with two-sided 80% confidence interval and one-sided p-values, will be obtained from the model for each visit. LS Mean change from baseline and two-sided 80% CI for each visit through Week 24 in blood eosinophils will be presented in figure.

Blood eosinophils count will be also summarised in shift tables comparing maximum value during treatment to baseline value for the ITT population.

Other exploratory biomarkers

The following serum and plasma biomarkers will be collected and summarised:

- Total IgE, allergen-specific IgE, sST2 (serum);
- Plasma EDN;
- CCI
- Serum IL-5;
- Serum IL-13;
- Serum TSLP.

Allergen-specific IgE status and Serum IL33:ST2 at baseline will be used for subgroup analysis of the primary endpoint (pre-BD FEV₁) as described in Section 4.2.4.3. The subgroup cut-off for Serum IL33:ST2 is the Serum IL33:ST2 baseline median.

All the above biomarkers, except allergen specific IgE will be summarised with descriptive statistics at each visit and change from baseline summarised for each post-baseline visit. Change from baseline in all the above biomarkers, except allergen specific IgE and Serum IL33:ST2 will be analysed using a MMRM as described in Section 4.1.2. Endpoints will be log transformed prior to analysis. LS Mean change from baseline and two-sided 80% CI for each analysed visit will be presented in figures.

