4.2.8.3 Exploratory analyses Analysis of Objective Cough

Observed values, percentage and relative change from baseline to Week 16 in objective cough measurements (see Section 3.6.2) will be summarised for ITT population.

Percentage and relative changes from baseline in objective cough measures at Week 16 will be analysed using an analysis of covariance model as described in Section 4.1.3 (reportable results for variables log-normally distributed). Objective cough measurements will be log-transformed prior to analysis. LS Mean change from baseline to Week 16, together with the two-sided 80% CI, in objective cough parameters will be presented in figure.

Cough VAS

Observed values and absolute change from baseline to Week 16 in cough VAS score will be summarised by visit for ITT population.

Change from baseline to Week 16 in cough VAS score will be analysed using an ANCOVA model as described in Section 4.1.3. LS Mean change from baseline to Week 16, together with the two-sided 80% CI, in cough VAS score will be presented in figure.

A listing including cough VAS score results will be produced for the ITT population.

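### SAP 4.1.3 does not move the baseline covariate to the log scale when the ANCOVA response is logged, so a literal reading costs the cough analysis some precision

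*SAP*

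**What the plan says.** SAP 4.1.3 defines the ANCOVA "for continuous endpoints collected at only one post-baseline visit". Treatment is a fixed effect, "with the baseline value, background medication use, geographic region and baseline ICS total daily dose as covariates". For log-normal variables it states that "if the parameter results to be log-normally distributed, the variable fitted in the model will be the change from baseline in logarithmical scale", and continues: "The ANCOVA model will be as described above but the reportable results from the model will be". The section does not give the scale of the baseline covariate in that case.

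SAP 4.1.2 has an almost identical paragraph for the MMRM. There the log-scale change is fitted "with the logarithm of the baseline value as a covariate".

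Objective cough frequency (daily, awake and night-time) is assigned to the ANCOVA: SAP 4.2.8.3 says the changes "will be analysed using an analysis of covariance model as described in Section 4.1.3", using the log-normal reporting. It adds: "Objective cough measurements will be log-transformed prior to analysis". The section specifies no log transformation for cough VAS.

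For sST2 the SAP names two models. Section 4.2.8.2 lists sST2 among biomarkers which, "except allergen specific IgE and Serum IL33:ST2 will be analysed using a MMRM as described in Section 4.1.2". Table 14.2.14.2 in the list of outputs gives ANCOVA for the same comparison.

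**The concern.** A change on the log scale is log follow-up minus log baseline. If the two logs are roughly bivariate normal, that change is linear in log baseline and not in the right-skewed raw baseline. A raw covariate therefore removes less of the between-participant variation. It also breaks a useful identity: with log baseline in the model, analysing log change or log Week 16 value gives the same treatment difference, and with raw baseline it does not.

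Because 4.1.2 needed an explicit clause to switch the covariate, its absence from 4.1.3 leaves two models open. Two programmers could report different estimates, intervals and p-values for the same table. The cough sub-study has little precision to spare: at most 60 participants, about 20 per arm, with a target that may not be reached (SAP 1.3), and recordings shorter than 18 hours are excluded (SAP 3.7).

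**Working it through.** **Figure in the plan.** None is given for cough or sST2; SAP 1.3 says that no power calculation was done for the sub-study. The one powered figure, at least 80% for pre-BD FEV₁, reproduces: 150/(420·√(2/72)) = 150/70 = 2.143; 2.143 − 1.282 = 0.861; power 80.5%. This point does not touch it.

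**Inputs.** The number per arm, about 20, is from SAP 1.3, and the one-sided 10% level is from SAP 4.1.3. The SD of log baseline (s) and the correlation of log baseline with log Week 16 (r) are not in the documents. I assume s = 0.6 to 1.2 and r = 0.4 to 0.7, with equal SDs at both visits and bivariate normal logs. The other covariates are left out.

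**Formulas.** Let X be log baseline and D the log change.
- Var(D) = 2s²(1 − r), and corr(D, X)² = (1 − r)/2.
- For raw baseline, corr(exp X, X)² = c² = s²/(exp(s²) − 1). Since D depends on baseline linearly through X, corr(D, exp X)² = c²(1 − r)/2.
- Residual variance, raw over log: VR = [1 − c²(1 − r)/2] / [1 − (1 − r)/2] = [2 − (1 − r)c²]/(1 + r).
- No baseline at all, over log: 2/(1 + r).

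**Example.** At s = 1.0 and r = 0.6: c² = 1/(2.718 − 1) = 0.582; VR = (2 − 0.4 × 0.582)/1.6 = 1.767/1.6 = 1.105.

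| s | r | c² | Variance, raw/log | SE, raw/log | 20 per arm worth | Variance, no baseline/log |
|---|---|---|---|---|---|---|
| 0.6 | 0.7 | 0.831 | 1.030 | 1.015 | 19.4 | 1.176 |
| 1.0 | 0.6 | 0.582 | 1.105 | 1.051 | 18.1 | 1.250 |
| 1.2 | 0.4 | 0.447 | 1.237 | 1.112 | 16.2 | 1.429 |

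The first and last rows are the extremes of the assumed range. On a wider grid (s 0.3 to 1.5, r 0.3 to 0.9) the variance ratio runs from 1.002 to 1.40.

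**Simulation** (6000 trials per scenario, three arms of 20 or 72, one-sided 10%).
- *Bias:* for an assumed 30% reduction the true difference is log 0.7 = −0.357. With 20 per arm, s = 1.0 and r = 0.5, the mean estimate was −0.356 under either covariate.
- *Type I error:* 9.5% to 10.9% over all scenarios, with a simulation standard error of √(0.1 × 0.9/6000) = 0.4 points.
- *Power, 20 per arm:* 47% with raw and 50% with log baseline at s = 1.0, r = 0.5; 30% and 33% at s = 1.5, r = 0.5.

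**sST2.** Protocol Table 2 schedules it at SV4 and SV10 only, and SAP Table 9 gives it one post-baseline window, Week 16. The one-visit rule in 4.1.3 and Table 14.2.14.2 therefore point to ANCOVA, while the text of 4.2.8.2 points to the MMRM.

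**The case against.** The strongest reply is that the SAP never says the covariate is raw. The gap is an omission, and for cough the endpoint text leans the other way. The SV2 baseline recording is itself an objective cough measurement, so a sentence that logs those measurements before analysis can fairly be taken to log the baseline as well. That reading stands as a possibility, so it would be too strong to say that the plan specifies raw baseline. It does not close the gap, because the same section sends the analyst to 4.1.3, which keeps its covariate list unchanged for the log case.

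A reader might infer three stronger things that are not supported:
- *That baseline adjustment is lost.* Raw baseline keeps the fraction c² of the variance that log baseline explains: about 83% at s = 0.6, 58% at 1.0 and 45% at 1.2. It remains better than no adjustment.
- *That a few heavy coughers would drive the adjusted difference.* Under the assumed normal model for the logs, the simulation shows an essentially unbiased estimate and type I error near 10%. What is shown is inefficiency.
- *That sST2 has the same defect.* The text of 4.2.8.2 gives it the MMRM, which uses log baseline. Its first problem is the conflict over which model applies.

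It is also fair to say that little hangs on this. Cough and sST2 are exploratory, and the primary and secondary analyses do not use the paragraph.

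**Conclusion.** The concern holds as a gap in wording with a small statistical cost. SAP 4.1.3 does not put the baseline covariate on the log scale as 4.1.2 does. Followed literally, the log-scale ANCOVA for cough frequency has 3% to 24% more variance than it need have, or about 1.5% to 11% in standard error. At s = 1.0 and r = 0.6 that is like losing about 2 of 20 participants per arm. These sizes rest wholly on the assumed SDs and correlations; if log baseline varies less, the loss can be negligible. If the analyst logs the baseline anyway, there is no loss. The sST2 conflict is a separate matter. This is a minor point, worth making because the better model costs nothing.

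**What to change.** In the log-normal paragraph of SAP 4.1.3, after the sentence that defines the log-scale response, add the clause already used in 4.1.2: "with the logarithm of the baseline value as a covariate". Separately, reconcile the sST2 model between SAP 4.2.8.2 and Table 14.2.14.2, bearing in mind its single scheduled post-baseline visit. Once 4.1.3 carries the clause, the baseline is logged whichever of the two is kept. The cost is one clause and one consistency edit in the SAP. Neither change needs new data or alters the design or sample size.
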